Cost-analysis on R-SS compared to laparoscopic multiport hysterectomy in benign gynecology has a knowledge gap. A retrospective study suggests increased cost per case using R-SS compared to laparoscopic multiport hysterectomy (7)(El Hachem et al. 2016). A variety of circumstances influences the analyses such as already established infrastructure for robotic surgery at the hospital, high volume versus low volume robotic centers and experienced robotic teams. Cost-effectiveness analyses are essential in order to provide a responsible utilization of health care resources and includes determination on sick-leave, consultation to healthcare (ex kontakt I amb ell e.l. pga kir.relatedede problemstilling). If out-of-hospital costs are included these may vary between countries; however, the phase between hospital stay and return to work may imply extra cost for the patient, need for reimbursement from health insurances, visits to medical professionals due to related morbidity a.s.o. If rehabilitation with RSS is shorter and includes less extra medical cost and visits the total cost may be less.

Summary:

R-SS hysterectomy is a novel technique, which may be superior to conventional laparoscopic multiport hysterectomy in select patients regarding sick-leave, cosmesis and postoperative pain. We, therefore, aimed at evaluating the learning curve using different robotic equipment (DaVinci Si Multiport surgical system and DaVinci Xi multiport and single site surgical system) in our cohort since 2014 to determine its applicability in our hospital setting. Secondly, we perform a randomized trial to compare R-SS hysterectomy with conventional laparoscopic multiport hysterectomy with regard to outcome postoperative rehabilitation, cosmesis, and the operational cost

Aim of study

Our study aims to evaluate R-SS with respect to:

Primary outcome:

- Length of hospital stay and time to return to daily activities /work
- Cosmesis; pre-and postoperative evaluation
- Postoperative pain (VAS)

Secondary outcome

- Learning curve for robotic-assisted hysterectomy including R-SS hysterectomy
- Patient satisfaction with the cosmesis
- Duration of operation incl. detailed information of time consumption of defined steps at hysterectomy, operation- and console time, blood loss, conversion rates, additional ports, port-site hernias, time at hospital, re-admission
- Cost-effectiveness analysis for the R-SS hysterectomy

Materials and Methods

Study 1:

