Detailed learning curves for robotic surgery- single site and multiport hysterectomy – a prospective, controlled study. A retrospective study of all robotic hysterectomy since 2014

The prospective controlled study compares R-SSH with robotic multiport hysterectomy (the controls) and will be performed at the Department of Gynecology, Herning Hospital, between September 2016 to end of December 2017. Sample size is estimated based on recommendations from the literature (8)(Cala V. et al. 2012). The study consists of two sub-studies (A and B). Each of the two sub-studies includes 40 procedures performed by two experienced laparoscopists with 20 procedures each.

A: Determination of learning curve for two similar experienced surgeons, for 40 robotic *multiport* hysterectomies – 20 hysterectomies per surgeon.

Inclusion criteria for the learning curve studies are hysterectomy on benign indication, ASA group 1 or 2, BMI (body mass in kg/heights in metres²) less than 35 kg/m² (for R-SS hysterectomy less than 30), uterine size less than 300 g estimated by ultrasound, using Ferraris formula.

Exclusion criteria are risk of adhesions, prior extensive abdominal surgery and prior midline incision, cutis laxa of abdomen surgery, endometriosis, and more than 1 cesarean section.

The procedure is video recorded and peri-and postoperative data are collected prospectively. Various steps during the procedure are determined such as various split time measurements like docking time, console time, vaginal cuff suturing, incision start, skin-to-skin and closure time. Uterine size and blood loss, as well as patient demographic data are registered.

B. The on-going study estimates the learning curve for *R-SS* hysterectomy. In- and exclusion criteria as for Study 1 except for inclusion criteria of BMI less than 30 kg/m²

C. Further, a retrospective cohort from the first robotic hysterectomies in 2014 until recently will be evaluated. The surgeries in the prospective studies are performed using the Da Vinci Xi surgical system and in the retrospective study using the Da Vinci Si Multiport system. Due to its design only crude incidences on perioperative variables will be evaluated.

Study 2

Robotic single-site hysterectomy compared to laparoscopic multiport hysterectomy – a prospective randomized controlled study; cosmetic satisfaction and surgical outcome.

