The study is scheduled to start May 2018 and compares R-SS hysterectomy to laparoscopic multiport hysterectomy. Procedures are performed by an experienced three-surgeon team. Patients are randomized to either laparoscopic multiport hysterectomy (N=62) or R-SS hysterectomy (N=62) by random numbers in sealed envelopes prepared by a third party. Eligibility criteria are the same as for study 2B (i.e. BMI < 30 kg/m²). Patient's satisfaction with body image and cosmesis is assessed at different time points pre- and postoperatively by means of multidimensional body-self relations questionnaire – appearance evaluation sub-scale and POSAS. Postoperative pain and analgesia use will

be registered as well as secondary outcome parameters as described above. A follow-up at one, three, and six month include self evaluation of the scar and registration of port-site hernias, vaginal dehiscence or other complications (Vercellia et al). Interviews and diaries will include time of return to home and work, daily activities including sexuality

The R-SS hysterectomy is performed using da Vinci, Xi robotic system. One single port, diameter 2 cm is applied at the umbilicus. Applying an additional assistant port is defined as conversion of procedure

The laparoscopic multiport hysterectomy is performed using our standard equipment and 4 trocars, 5 mm each.

Study 3

Socio-economical consequences of R-SS hysterectomy versus conventional laparoscopic hysterectomy

Study details in preparation

Instrumental cost

Hospital stay

Post-hospitalization cost. sick days, extra visits to the out-patient clinic, general practitioner, medical expenses

Sample size calculation was based a PhD- study on fast track hysterectomy, which showed a difference in return to work of 4 days and SD ± 8 . 62 women in each group are needed for a power of 80% (beta=0.2) to replicate this study. To include those not working, we calculated that with an expected VAS of 0.86 ± 0.2 and 62 in each group the sample was sufficient to detect a difference of 0.1 in VAS; still, with a power of 80%. All calculations are based on two-sided testing with alpha = 0.05.

The retrospective study was approved by the Data Authority (no. 1-16-02-913-17). The randomized trial is registered at clinicaltrials.gov (NHS).

Statistics

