For statistical calculations of proportions the χ^2 -test with Yates' correction for discontinuity or the Fisher's Exact-test was used. For continuous variables Student's t-test, Mann-Whitney's U -test, and Wilcoxon's Signed Rank test was used when appropriate.

Questionnaires with partial answers were included in the calculations, if possible. ANOVA and Kruskal Wallis' test was performed between group variables. Post-hoc test with Newman-Keul's test was performed between group pairs, if ANOVA was significant.

Repeated measurements were evaluated with 2-way ANOVA and surgical procedure as group variable with potential confounding variables like age, BMI, surgeon, and additional surgery added. The distribution of BMI, age, blood loss, split times during operation, hospital stay and time of return to daily activities and work were evaluated by means of Kaplan-Meyer analysis. The level of significance was a two-sided $p < 0.05$. Logistics regression analysis was performed with surgical procedure as dependent variable and the various split times, surgeon, age, BMI, parity, as independent variables. Learning curves were established for each individual surgeon, surgical procedures, and combined

monitored over time of the studies. Data are given as mean \pm SD if following Gaussian distribution and median (minimum, maximum) if non-Gaussian distributed. IBM SPSS Statistics 20 was used as the statistical software

Research plan

Study 1; jan 2017-june 2018

Study 2; may. 2018-jan. 2020

Study 3; 2020-2021

Responsibility:

[name] [name], [name]. Department of Gynecology and Obstetrics, Herning Hospital, Principal data supervisor and investigator for clinicaltrials.gov
[name], Ph.D. Department of Gynecology and Obstetrics, Herning Hospital

References

El Hachem, L., et al. (2016). "Robotic Single-Site and Conventional Laparoscopic Surgery in Gynecology: Clinical Outcomes and Cost Analysis of a Matched Case-Control Study." *J Minim Invasive Gynecol* **23**(5): 760-768.

Golkar, F. C., et al. (2012). "Patients' perceptions of laparoendoscopic single-site surgery: the cosmetic effect." *Am J Surg* **204**(5): 751-761.

Sandberg, E. M., et al. (2017). "Laparoendoscopic single-site surgery versus conventional laparoscopy for hysterectomy: a systematic review and meta-analysis." *Arch Gynecol Obstet* **295**(5): 1089-1103.

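### The logistic regression is the wrong way round: surgical procedure is the response and the operative times it produces are predictors, so it cannot give an adjusted difference in operating time

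*Protocol*

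**What the plan says.** The Statistics section of the protocol specifies one logistic regression: "Logistics regression analysis was performed with surgical procedure as dependent variable and the various split times, surgeon, age, BMI, parity, as independent variables". It does not say whether the model serves Study 1, Study 2 or both.

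Other sections fix where these variables belong:

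- **Aim of study, secondary outcome:** the list includes "Duration of operation incl. detailed information of time consumption of defined steps at hysterectomy, operation- and console time, blood loss". The Study 2 text carries this list into the randomized trial by referring to "secondary outcome parameters as described above".
- **Study 1:** steps are timed while the operation is under way, as "various split time measurements like docking time, console time, vaginal cuff suturing" and others. The BMI ceiling is 35 kg/m² in general but "for R-SS hysterectomy less than 30". Also, "Each of the two sub-studies includes 40 procedures performed by two experienced laparoscopists with 20 procedures each".
- **Study 2:** procedure is allocated by random numbers in sealed envelopes, 62 women to each arm.
- **Statistics, repeated measures:** "Repeated measurements were evaluated with 2-way ANOVA and surgical procedure as group variable", with confounders added. This model has procedure on the explanatory side, but it is written for repeated measurements.

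Split times are otherwise named only in the Kaplan-Meier sentence. The general t-test and Mann-Whitney sentence covers them without adjustment.

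**The concern.** An outcome model explains what happened by what was done. Here the procedure is the quantity explained, and times that exist only because a procedure was carried out explain it.

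In Study 2 allocation is random, so age, BMI, parity and surgeon can predict it only by chance. The only predictors with real content are outcomes. It is not a propensity model either, since that would hold only variables known before surgery.

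In Study 1 procedure is set by sub-study, so some coefficients describe the design and not the surgery.

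At stake is the adjusted comparison of duration. No other sentence in the protocol gives a covariate-adjusted model with operating time as the dependent variable. This matters most in non-randomized Study 1. The odds ratios that the model would produce are also easy to misread as effects of surgery.

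**Working it through.** **Inputs.** From the protocol: 62 per arm in Study 2; 40 procedures per sub-study in Study 1, 20 per surgeon; BMI limits of 35 and 30. The 62 reproduces from the protocol's own difference of 4 days and SD of 8: the normal approximation gives 63 per group, and 79.5% power at 62. The protocol gives no difference or SD for operating time and no BMI distribution, so those below are assumptions. Results are from 2,000 simulated trials per scenario, with age, BMI, parity and a three-level surgeon as covariates in the 62-per-arm scenarios.

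**1. One time shared by both arms.** If time is normal with the same SD in both arms and a mean difference d, the log odds of procedure rise by d/SD² per minute. The coefficient therefore mixes the difference with the spread. For d = 10 minutes:

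| SD (min) | d/SD² | Mean logit coefficient | Odds ratio per min | Reversed model significant | Linear estimate (min) | Linear model significant |
|---|---|---|---|---|---|---|
| 15 | 10/225 = 0.0444 | 0.0478 | 1.049 | 94.7% | 9.96 | 94.6% |
| 20 | 10/400 = 0.0250 | 0.0274 | 1.028 | 78.7% | 10.15 | 78.1% |
| 25 | 10/625 = 0.0160 | 0.0173 | 1.017 | 58.6% | 10.07 | 58.0% |
| 30 | 10/900 = 0.0111 | 0.0121 | 1.012 | 45.2% | 10.01 | 44.6% |

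Detection is the same in both directions; the effect measure is not. Different truths also give similar answers: 10 minutes with SD 20 gives 10/400 = 0.0250 and 20 minutes with SD 30 gives 20/900 = 0.0222. A separate set of 1,000 simulations put these odds ratios at 1.027 and 1.024.

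**2. Several times entered together, as the sentence allows.** Let total time be two components (SD 7 each) plus a remainder (SD 12). Once the components are in the model, the total-time coefficient reflects only the remainder: its share of the difference divided by 12² = 144.

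| Where the 10 minutes lie | Expected coefficient | Simulated | Significant | Linear model of total time (min) |
|---|---|---|---|---|
| In the components | 0/144 = 0 | 0.0006 | 5% | 10.09 |
| Spread evenly over the three parts | 3.33/144 = 0.023 | 0.0254 | 29% | 9.98 |
| In the remainder | 10/144 = 0.069 | 0.0771 | 99.5% | 10.03 |

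**3. Robot-only times in Study 2.** The laparoscopic arm has no docking or console time. Left missing, these times leave 62 complete cases against 0. Coded as 0, they separate the arms completely: every laparoscopic value was 0, the smallest simulated R-SS console time was 27 minutes, no finite estimate exists, and the software reported standard errors above 40,000.

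**4. Study 1.** If the same two surgeons operate in both sub-studies, the crude surgeon odds ratio is (20/20)/(20/20) = 1 by design. For BMI, both groups of 40 were drawn from one population and cut at 35 and 30. With mean (SD) 25 (4), 26 (4.5) and 27 (5), the entry limits alone gave odds ratios per kg/m² of 0.936, 0.906 and 0.881, significant in 13.8%, 30.0% and 50.4% of runs. A rerun with BMI as the only predictor gave somewhat weaker values: 0.943, 0.918 and 0.897, significant in 14%, 27% and 43%.

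**The case against.** The strongest reply is that little is lost. With a single shared time the reversed model detects a difference as often as linear regression. The plan already reports means with SD or medians, with unadjusted tests, so minutes will be available. In randomized Study 2 the unadjusted difference is unbiased and adjustment is optional. The protocol nowhere promises an adjusted difference in duration. All of this is true and limits the severity. It does not rescue the model: the sentence evidently intends adjustment for surgeon, age, BMI and parity, and as written it cannot deliver that for duration. The reply is weakest in Study 1, where there is no randomization.

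Further points stand in part:

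- The wording on split times echoes the Study 1 text, where both procedures are robotic. The breakdown with docking or console time is therefore conditional on the model being used in Study 2 with those times entered. The sentence does not exclude this.
- The instability in step 2 comes from conditioning on components as well as from the reversal, so it is not evidence about direction alone.
- The BMI limits are a design feature. Exchanging the roles does not create overlap between 30 and 35 kg/m²; it only stops the entry rule from being reported as a result.
- The size of every effect shown rests on assumed SDs and illustrates the defect without measuring it in this trial.

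**Conclusion.** The concern holds. In either study procedure precedes the split times, and duration is a listed secondary outcome, so response and predictor are exchanged. This rests on the protocol's text alone.

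The main consequence is a wrong effect measure: under the assumed 10-minute difference, an odds ratio per minute anywhere from 1.049 to 1.012 depending on the SD, against about 10 minutes from the linear model. With overlapping times entered together, the total-time result can range from null to almost always significant for the same total difference. With robot-only times in Study 2 the model cannot be estimated.

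The primary outcomes, the sample size and the unadjusted comparisons of duration are unaffected. It should be corrected, but it does not threaten the trial's main conclusions.

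**What to change.** Rewrite the sentence so that total operating time and each split time is, in turn, the dependent variable of a linear model (log scale if skewed). Procedure is the explanatory factor, and surgeon, age, BMI and parity are covariates. Report the adjusted difference with its 95% CI, and state that the models are fitted separately for Study 1 and Study 2. Compare docking and console times only between robotic procedures (Study 1), and describe them within the R-SS arm in Study 2.

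That is enough to correct the reversal. Three additions are useful but separable: the same model for blood loss; a Study 1 sensitivity analysis limited to BMI below 30 kg/m², where both procedures were open; and logistic regression kept for binary outcomes such as conversion or readmission, with procedure as an independent variable. Because modelling each step adds comparisons, total operating time could be named as the lead duration result and the steps given as estimates with intervals.

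The core change is a rewrite of one sentence in the Statistics section. Data, software, sample size and primary analyses stay as they are; the optional models add a little analysis time.
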